### 11.2.3.2 Primary Analysis

If a different group of healthy matched control subjects are needed to match the mean age and BMI for the RI and ESRD groups, then separate analyses will be performed for the populations as follows:

- Mild RI and moderate RI versus an appropriate group of healthy matched control subjects;
- Severe RI versus an appropriate group of healthy matched control subjects;
- ESRD subjects (non HD and HD) versus an appropriate group of healthy matched control subjects.

If a single set of healthy matched control subjects can be used for comparison with all RI and ESRD groups, the following analysis will be used.

Separately for each pharmacokinetic parameter, individual values of AUC0- $\infty$ , AUC0-last, AUC0-24, Ceoi (Cmax), and CL will be natural log-transformed and evaluated with a linear fixed-effects model containing a categorical effect for populations. The REPEATED statement with the GROUP=Population option will be used in SAS PROC MIXED to estimate separate variances for each population. The Kenward and Roger adjustment will be used to calculate the denominator degrees of freedom for the fixed-effect (DDFM=KR).

Ninety-five percent (95%) confidence intervals for the least squares means for each population will be constructed on the natural log scale and will reference the t-distribution. Exponentiating the least-squares means and their corresponding 95% confidence intervals will yield estimates for the population geometric means and confidence intervals about the geometric means on the original scale.

To compare subjects with RI in each of the renal categories (mild RI, moderate RI, severe RI, ESRD nonHD and ESRD HD) to matching subjects with normal renal function, a two sided 90% confidence interval for the true difference in means (RI/normal renal function) will be calculated for each PK parameters (AUC0- $\infty$ , AUC0-last, AUC0-24, Ceoi (Cmax), and CL) using the mean square error from the model and referencing a t-distribution. For each of the RI populations, these confidence limits will be exponentiated to obtain the 90% confidence interval for the true ratio of geometric means (RI/normal renal function) for each pharmacokinetic parameter.

Figures showing individual pharmacokinetic values with GMs (95% confidence intervals) by population, plotted on the natural log scale, will be provided for AUC0- $\infty$ , AUC0-last, AUC0-24, Ceoi (Cmax), and CL.

Individual values will be listed for each pharmacokinetic parameter (AUC0-∞, AUC0-last, AUC0-24, Ceoi (Cmax), Tmax, elimination terminal t1/2, CL, Vz, and Fe) by population, and the following (non-model-based) descriptive statistics will be provided: N (number of subjects with non-missing data), arithmetic mean, standard deviation, arithmetic percent CV (calculated as 100 x standard deviation/arithmetic mean), median, minimum, maximum, geometric mean, and geometric percent CV (calculated as 100 x sqrt( exp(s) - 1), where s is the observed variance on the natural log-scale).

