The data from the already enrolled healthy subjects who satisfy the gender, mean age and BMI matching criteria of the RI subjects in each Panel (C and E) will be used. However, if any of the healthy subjects do not meet the matching criteria described above, additional healthy subjects will be enrolled to result in a total of 8 healthy subjects who match the mean age ( $\pm 15$  years) and the mean BMI ( $\pm 10\%$ ) of each Panel C and E. The gender of the additional healthy subject(s) will be selected to ensure that there is a minimum of 2 subjects of each gender in the group of subjects within Panel D who match with Panels C and E.

The pharmacokinetic comparisons between each renally impaired panel (Panels A, B, C, and E) and healthy controls will include only the control subjects who meet the matching criteria for the respective RI panel.

In both Parts, MK-3866 will be administered IV over 30 minutes ( $\pm 5$  minutes).

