### 11.2.1 Determination of Sample Size

The sample size selected for each population to evaluate the effect of RI on the pharmacokinetic of MK-3866 was not chosen to satisfy any a priori statistical requirement. This sample size (N=8 per group) has historically been shown to be sufficient for studies of this type and should provide adequate data to support the planned analyses. Nevertheless, estimates of the expected precision of the estimates, based on these sample sizes are presented below.

The precision of the estimates of ratios of geometric means obtained from this study can be assessed by calculating the half-width of the 90% confidence intervals expected for the given sample size and assumed variability. The estimated between-subject variance for log AUC0-∞ is 0.0196 log ng\*hr/mL from the FIH study (PN001). Since the between subject variability in subjects with severe RI has historically been seen to be 2-3 fold higher in many studies, the between subject variability obtained from healthy subjects was inflated by a factor of 2 for subjects with severe RI and was used for the following calculations. With 8 renally impaired subjects and 8 healthy matched subjects, the half-width of the 90%

confidence interval for the arithmetic mean  $AUC_{0-\infty}$  on the log scale will be  $0.151 \log \text{ng}^* \text{hr}/\text{mL}$ . The lower and upper 90% confidence limits for the true ratio of geometric means will be given by  $\text{OBS}/1.163$  and  $\text{OBS} \times 1.163$ , where OBS is the observed ratio of geometric means. Thus, for example, if the observed ratio of geometric means was 1.5, the 90% confidence interval would be (1.29, 1.74).

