### 11.2.3 Analysis Overview

#### 11.2.3.1 Interim analysis

An interim statistical analysis of the pharmacokinetic data obtained in moderate RI subjects will be performed, including a comparison with data in healthy control subjects from this study.

For this interim statistical analysis, values for the pharmacokinetic parameters  $AUC_{0-\infty}$ ,  $AUC_{0-\text{last}}$ ,  $AUC_{0-24}$ , and  $C_{\text{eoI}} (\text{C}_{\text{max}})$  of MK-3866 will be estimated and compared to concurrent healthy control subjects. A Linear Fixed Effects (LFE) Model will be used for the analysis of natural log-transformed pharmacokinetic parameters:  $AUC_{0-\infty}$ ,  $AUC_{0-\text{last}}$ ,  $AUC_{0-24}$ , and  $C_{\text{eoI}} (\text{C}_{\text{max}})$  separately. The LFE model will contain a categorical factor for population (moderate RI and healthy control subjects), and possible covariates for age, gender, and BMI, if statistically significant. A two-sided 90% confidence interval for the mean differences of  $AUC_{0-\infty}$ ,  $AUC_{0-\text{last}}$ ,  $AUC_{0-24}$ , and  $C_{\text{eoI}} (\text{C}_{\text{max}})$ , of MK-3866 will be calculated based on the above model. These confidence limits will then be exponentiated to

obtain confidence intervals for the GMR (moderate RI /healthy) for AUC0- $\infty$ , AUC0-last, AUC0-24, and Ceoi (Cmax) of MK-3866. Individual and mean concentrations versus time plots profiles will be also be provided.

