model, which is described in the primary analysis. Ninety-five percent (95%) confidence intervals for the least squares means for each population will be constructed. To compare subjects with RI in each of the renal categories (mild RI, moderate RI, severe RI, ESRD nonHD and ESRD HD) to matching subjects with normal renal function, a two sided 90% confidence interval for the true difference in means (RI/normal renal function) will be calculated for each urine pharmacokinetic parameter (Ae0-24, Fe and CLr).

Individual values will be listed for each urine pharmacokinetic parameter (Ae0-24, Fe and CLr) by population, and non-model-based descriptive statistics will be provided.

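### Does the mean-square-error wording in Section 11.2.3.2 undermine the unequal-variance confidence intervals for the primary ratios?

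*Combined protocol and SAP*

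**What the plan says.** Section 11.2.3.2 analyses the log-transformed plasma parameters with population as a categorical effect. On the variance structure it is explicit: "The REPEATED statement with the GROUP=Population option will be used in SAS PROC MIXED to estimate separate variances for each population". Denominator degrees of freedom are Kenward-Roger (DDFM=KR). Two paragraphs later, the two-sided 90% interval for each of the five renal categories against normal renal function is to be calculated "using the mean square error from the model and referencing a t-distribution".

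This model is introduced for the case where one set of healthy controls "can be used for comparison with all RI and ESRD groups, the following analysis will be used". If the controls do not match every panel, the section provides separate analyses for mild with moderate, for severe, and for ESRD. Section 9.1 allows for that outcome in Panels C and E: "additional healthy subjects will be enrolled to result in a total of 8 healthy subjects who match the mean age".

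Two comparable intervals are described without naming a mean square error. The interim interval in Section 11.2.3.1 is for parameters "of MK-3866 will be calculated based on the above model", and the urine parameters in Section 11.2.3.3 (Objective 2) use the "model, which is described in the primary analysis". The mean-square-error phrase does recur in Section 11.2.3.3 (Objective 1), after an unstructured covariance matrix has been specified.

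**The concern.** With one residual variance per population, the variance of a contrast is s²(RI)/n(RI) + s²(healthy)/n(healthy). No common error term exists, so the interval sentence conflicts with the model two paragraphs above it.

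The intervals are the reported precision for all five primary estimations. A reader who acted on the sentence by pooling one variance over all populations would make each panel's interval depend on the scatter in unrelated panels. The protocol itself expects unequal scatter: Section 11.2.1 says that "the between subject variability in subjects with severe RI has historically been seen to be 2-3 fold higher in many studies". Pooling would then discard what the GROUP option is there to protect, and the severe panel is where an interval that is too narrow would matter most.

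**Working it through.** **Inputs.** From Section 11.2.1: variance of log AUC0-∞ in healthy subjects 0.0196; severe RI inflated by 2 (historically 2 to 3); 8 per group; 90% two-sided. The variances for mild, moderate and ESRD are not given, so every value used for them below is an assumption.

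**1. The plan's own figure.** Half-width = t(0.95; 14) × √(0.0196/8 + 0.0392/8) = 1.7613 × √0.00735 = 0.151. Then exp(0.151) = 1.163, and an observed ratio of 1.5 gives 1.5/1.163 = 1.29 and 1.5 × 1.163 = 1.74. All three stated figures reproduce. A two-group pooled error gives the same result: (0.0196 + 0.0392)/2 = 0.0294 and √(2 × 0.0294/8) = √0.00735. The sample-size section therefore cannot show which error term was meant.

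**2. The model as specified.** Half-width = t(0.95; df) × √(v₁/8 + v₂/8), with df = (v₁ + v₂)²/(v₁²/7 + v₂²/7), the Satterthwaite formula as a stand-in for Kenward-Roger.
- Panel at the healthy variance: 14 df, 1.7613 × 0.0700 = 0.1233.
- Severe ×2: 12.6 df, 1.7752 × 0.0857 = 0.1522.
- Severe ×3: 11.2 df, 1.7930 × 0.0990 = 0.1775.

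**3. What pooling would do: one control set, six populations of 8.** Half-width = t(0.95; 42) × √(2 × MSE/8), with t = 1.6820 and MSE the mean of the six variances. Percentages compare this with step 2.

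| Assumed variances | MSE | Pooled half-width | Severe | Mild, moderate | ESRD |
|---|---|---|---|---|---|
| (a) only severe ×2 | 0.02287 | 0.1272 | −16% | +3% | +3% |
| (a) only severe ×3 | 0.02613 | 0.1360 | −23% | +10% | +10% |
| (b) severe ×2, ESRD ×1.5 | 0.02613 | 0.1360 | −11% | +10% | −2% |
| (b) severe ×3, ESRD ×1.5 | 0.02940 | 0.1442 | −19% | +17% | +4% |
| (c) severe and ESRD ×2 | 0.02940 | 0.1442 | −5% | +17% | −5% |
| (c) severe and ESRD ×3 | 0.03920 | 0.1665 | −6% | +35% | −6% |
| (d) all impaired panels ×2 | 0.03593 | 0.1594 | +5% | +5% | +5% |
| (d) all impaired panels ×3 | 0.05227 | 0.1923 | +8% | +8% | +8% |

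Coverage of the nominal 90% interval (100,000 simulations per scenario, populations taken as independent):
- Pooled, (a): severe about 85% (×2) and 82% (×3).
- Pooled, (b): severe about 88% and 85%.
- Pooled, (c): severe and ESRD about 90%, mild and moderate about 95% to 98%.
- Pooled, (d): about 93% to 94% throughout.
- Separate variances, as specified: 90.0% to 90.5% in every scenario.

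For an observed severe ratio of 1.5 at ×2, the specified model gives (1.29, 1.75). Pooling gives (1.32, 1.70) under (a) and (1.30, 1.73) under (c).

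**4. What pooling would do: separate control sets.**
- Severe with healthy: 0.1510 against 0.1522 at ×2 (−1%); 0.1744 against 0.1775 at ×3 (−2%).
- Mild, moderate and healthy, all at 0.0196: t(0.95; 21) = 1.7207, so 1.7207 × 0.0700 = 0.1205 against 0.1233 (−2%).
- ESRD (two conditions) with healthy: 0.1391 against 0.1382 at ×1.5 (+0.6%); 0.1555 against 0.1522 at ×2 (+2%); 0.1840 against 0.1775 at ×3 (+4%).

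The small mild and moderate figure needs those two panels to share a variance. With mild at 0.0196 and moderate at ×2, MSE = (2 × 0.0196 + 0.0392)/3 = 0.02613 and the pooled half-width is 1.7207 × √(2 × 0.02613/8) = 0.1391. That is 13% above 0.1233 for mild and 9% below 0.1522 for moderate.

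**The case for a change.** The case for an edit is that the contradiction is real, sits in the primary analysis, and could be removed with one phrase. The sample-size calculation does not settle the reading. Under the least favourable assumptions, pooling would drop coverage for severe RI to about 82%. Because the direction and size of the error depend on unknown variances, one can argue that the choice should not be left open.

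Two parts of this stand: the phrase is wrong for this model, and step 3 is the right arithmetic for someone who pools. What does not stand is that the choice is open. The section names the procedure, the statement, the option, its purpose and the degrees-of-freedom method, and it takes the error term from that model. To pool, the analyst would have to remove GROUP=Population and fit something else, and Section 11.2 requires a departure from the stated analysis to be listed and explained in the study report.

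The recurrence of the phrase after an unstructured covariance, where it cannot redefine the model either, points to carried-over wording. That is supporting evidence only: with complete pairs, a paired error term there could give the same interval, which is not true of pooling in the primary analysis.

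**Conclusion.** No change to the plan is needed; this is a clerical slip. An analyst who requests each population contrast from the specified PROC MIXED fit gets the group-specific standard error with Kenward-Roger degrees of freedom, and coverage of about 90% under every variance pattern tried. Tidying the phrase would be harmless but would alter no estimate, interval or conclusion.

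The discrepancies are hypothetical twice over: they need a departure from the specified model, and then particular variances for mild, moderate and ESRD that the documents do not supply. The worst case, a severe-panel interval 23% too narrow, needs severe RI inflated threefold while ESRD stays at the healthy value. With ESRD inflated like severe RI, coverage for both is essentially nominal and the mild and moderate intervals err on the wide side. With separate control sets the effect is about 4% or less when the impaired groups in each analysis share a variance, and 9% to 13% in the twofold mild-versus-moderate example. The objectives are estimations with no equivalence bound, so even then no stated decision would turn on it.

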### 11.2.3.3 Secondary Analysis

#### Objective 1

To evaluate the extent to which MK-3866 is removed from plasma by HD, a linear mixed effect model with population (ESRD non HD, ESRD HD) as a fixed effect will be used. An unstructured covariance matrix will be used to allow for unequal treatment variances and to model the correlation between the two treatment measurements within each subject via the REPEATED statement in SAS PROC MIXED. Kenward and Roger's method will be used to calculate the denominator degrees of freedom for the fixed effects (DDFM=KR).

A natural log transformation will be applied to CL, AUC0-∞, AUC0-last, and Ceoi (Cmax). For each pharmacokinetic parameter, 95% confidence intervals for the least squares mean will be constructed on the natural log scale and will reference the t-distribution.

Exponentiating the least-squares means and their corresponding 95% confidence intervals will yield estimates for the population geometric means and confidence intervals about the geometric means on the original scale.

A two sided 90% confidence interval for the true difference in means (ESRD HD - ESRD non HD) will be calculated for each pharmacokinetic parameter (AUC0-∞, AUC0-last, Ceoi [Cmax], and CL) using the mean square error from the model and referencing a t-distribution. These confidence limits will be exponentiated to obtain the 90% confidence interval for the true ratio (GMR) of geometric means (ESRD HD / ESRD non HD) for each pharmacokinetic parameter.

Plots with individual ratios overlaid with GMR and corresponding 90% confidence interval will be provided for CL, AUC0-∞, AUClast, and Ceoi (Cmax).

Individual listings and descriptive statistics for CLD, plasma, CLD, dialysate, AD, AD(%dose), AUCD, AUC(1-4.5)Ca, AUC(1-4.5)Cv following a single-dose administration of MK-3866 will be provided for subjects with ESRD receiving HD.

Individual listings and descriptive summary statistics may be provided for CLr for those ESRD subjects in whom it is possible to determine CLr.

#### Objective 2

Separately for each urine pharmacokinetic parameter, where possible, individual values of Ae0-24, Fe and CLr will be natural log-transformed and evaluated with a linear fixed-effects

model, which is described in the primary analysis. Ninety-five percent (95%) confidence intervals for the least squares means for each population will be constructed. To compare subjects with RI in each of the renal categories (mild RI, moderate RI, severe RI, ESRD nonHD and ESRD HD) to matching subjects with normal renal function, a two sided 90% confidence interval for the true difference in means (RI/normal renal function) will be calculated for each urine pharmacokinetic parameter (Ae0-24, Fe and CLr).

Individual values will be listed for each urine pharmacokinetic parameter (Ae0-24, Fe and CLr) by population, and non-model-based descriptive statistics will be provided.

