- q. During HD, blood samples for MK-3866 will be collected from both the pre-dialyzer and post-dialyzer blood lines; thus 2 plasma samples per time point during HD will be taken. A blood sample (a pre-dialyzer and post-dialyzer) will also be obtained immediately before the HD is stopped, if this time point does not coincide with a time point that is already scheduled.
- r. Dialysate samples for determination of MK-3866 will be obtained pre-dialysis, post-dialysis (before the HD is stopped), and for 1 minute every half hour during HD.
- s. HD session will be initiated immediately following the 0.5-hour postdose blood draw.

Abbreviations: ConMed = Concomitant Medication, CRU = Clinical Research Unit, FU = Follow-Up, FSH = Follicle Stimulating Hormone, HIV = Human Immunodeficiency Virus, IV = Intravenous, HD = Hemodialysis P = Predose, RI = Renal Impairment, S = Screening, UA = Urinalysis

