### **8.1.2 Secondary**

Objective 1: To investigate the extent to which MK-3866 is removed by HD.

Estimation 1: The extent to which MK-3866 is removed by HD from the plasma (e.g., Ca, Cv, AUCD, AUC[1-4.5]Ca, AUC[1-4.5]Cv, and CLD,plasma) or the dialysate (e.g., CD, AD, rr, AD,total, and CLD,dialysate) will be estimated.

Objective 2: To compare the urine pharmacokinetics (e.g., Ae0-24, Fe, and CLr) of MK-3866 following a single IV dose of MK-3866 to subjects with varying degrees of RI, where possible, to those of healthy matched control subjects.

Estimation 2: The Ae0-24, Fe, and CLr following a single IV dose of MK-3866 administered to subjects with varying degrees of RI, as appropriate, will be estimated and compared to those estimated in mean healthy matched control subjects.

Objective 3: To evaluate the safety and tolerability of the administration of a single IV dose of MK-3866 in subjects with varying degrees of RI.

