## **8.2 Analysis Endpoints**

### **Pharmacokinetics:**

#### **Part 1 and Part 2**

The pharmacokinetic parameters AUC0-∞, AUC0-last, AUC0-24, Ceoi (Cmax), Tmax, elimination terminal  $t_{1/2}$ , CL, and Vz in plasma, and Ae0-24, Fe, and CLr in urine, as appropriate, for MK-3866 will be computed.

## Part 2

In addition, in Part 2, the following pharmacokinetic parameters will be calculated during HD for plasma MK-3866: Ca, Cv, AUCD, AUC(1-4.5)Ca, AUC(1-4.5)Cv, and CLD,plasma and for dialysate MK-3866: CD, AD, rr, AD,total, and CLD,dialysate.

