#### Part 2:

Subjects will receive a single IV infusion of 200 mg MK-3866 at Hour 0 on Day 1, immediately after completion of the scheduled HD (Period 1), and at Hour 0 on Day 1, approximately 30 minutes prior to initiation of the scheduled HD (Period 2).

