### 11.1.3 Hemodialysis: Plasma and Dialysate

For subjects in Panel E, the following pharmacokinetic parameters for plasma MK-3866 will be calculated as appropriate:

Ca: Concentration in plasma entering the dialyzer line (arterial or pre-dialyzer line)

Cv: Concentration in plasma exiting the dialyzer (venous or post-dialyzer line)

AUCD: Plasma AUC values determined from Ca versus time profile during the dialysis period (0.5-4.5 hours) using 'linear up, log down' calculation method option in WinNonlin

AUC(1-4.5)Ca: Plasma AUC values determined from Ca versus time profile during the dialysis period from 1 hour to 4.5 hours using 'linear up, log down' calculation method option in WinNonlin

AUC(1-4.5)Cv: Plasma AUC values determined from Cv versus time profile during the dialysis period from 1 hour to 4.5 hours using 'linear up, log down' calculation method option in WinNonlin

CLD,plasma: Dialysis clearance based on plasma, calculated as  $Q \times R \times (AUC[1-4.5]Ca - AUC[1-4.5]Cv) / AUC(1-4.5)Ca$ , where Q is the flow rate of blood through the dialyzer, and R is the ratio of blood drug concentration to plasma drug concentration

For subjects in Panel E, the following pharmacokinetic parameters for dialysate MK-3866 will be calculated as appropriate:

CD:	Concentration in dialysate samples
AD:	Amount of drug recovered from each dialysate collection, calculated as: CD x dialysate volume
rr:	Rate of drug removal, calculated as: (CD x dialysate flow rate)
AD,total:	Cumulative amount of drug recovered from the dialysate will be obtained by integrating the rr versus time profile over the dialysis session duration, using actual times relative to the start time of dialysis
CLD,dialysate:	HD clearance based on dialysate, calculated as: AD,total/AUCD

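### Does leaving the session amount AD,total out of the hemodialysis reporting list put the dialysis-removal result at risk?

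*Combined protocol and SAP*

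**What the plan says.** Section 11.1.3 defines two dialysate amounts. AD is the "Amount of drug recovered from each dialysate collection, calculated as: CD x dialysate volume". For AD,total the text reads "Cumulative amount of drug recovered from the dialysate will be obtained by integrating the rr versus time profile over the dialysis session duration". Dialysate clearance is built on the second: "HD clearance based on dialysate, calculated as: AD,total/AUCD".

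The sampling scheme is in footnote r of the Part 2 flow chart (section 6.2). Dialysate samples "will be obtained pre-dialysis, post-dialysis (before the HD is stopped), and for 1 minute every half hour during HD".

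Both amounts are named side by side in Secondary Estimation 1 (section 8.1.2), "or the dialysate (e.g., CD, AD, rr, AD,total, and CLD,dialysate) will be estimated", and among the Part 2 endpoints (section 8.2), "for dialysate MK-3866: CD, AD, rr, AD,total, and CLD,dialysate". The Key Assessments in the synopsis also name both.

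The reporting sentence under Objective 1 in section 11.2.3.3 covers "Individual listings and descriptive statistics for CLD, plasma, CLD, dialysate, AD, AD(%dose), AUCD", followed by AUC(1-4.5)Ca and AUC(1-4.5)Cv. AD,total is not in it. AD(%dose) appears there and nowhere else.

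**The concern.** Secondary Objective 1 asks how much drug hemodialysis removes. The amount recovered over the session, and that amount as a percent of dose, are its most direct description. Taken with the definitions in section 11.1.3, the reporting list appears to tabulate the drug found in short samples and to drop the drug removed by the session. A percent of dose computed from those samples would be a small fraction of the true removal. A reader who took it for the session figure would conclude that dialysis clears almost nothing. The study is meant to inform dosing with respect to hemodialysis (section 7.2.1), so that would be an unfortunate number to misread.

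**Working it through.** **Step 1. Which quantities does the list contain?** CLD,plasma, CLD,dialysate, AUCD, AUC(1-4.5)Ca and AUC(1-4.5)Cv each have one value per subject. The quantities measured repeatedly during the session (Ca, Cv, CD and rr) are all absent, although section 8.2 names them too. A per-collection AD would be the only time-indexed entry, and the sentence gives no time index for summarizing it. The natural reading is that AD stands loosely for AD,total, and AD(%dose) for AD,total as a percent of dose.

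**Step 2. Can AD,total be lost?** No. Section 11.1.3 gives CLD,dialysate = AD,total / AUCD, so CLD,dialysate cannot be produced without AD,total. Rearranged:

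AD,total = CLD,dialysate × AUCD.

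Both factors are in the individual listings, so the session amount follows for each of the 8 planned Panel E subjects. The identity holds whatever interval AUCD covers, because the same AUCD is divided by and then multiplied back.

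**Step 3. What else depends on the label?**
- The ESRD HD/non-HD geometric mean ratios use CL, AUC0-∞, AUC0-last and Ceoi. No dialysate amount enters.
- CLD,plasma uses blood flow, the blood-to-plasma ratio and the two 1-to-4.5-hour AUCs. No dialysate amount enters.
- CLD,dialysate uses AD,total by definition, not AD.

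**Step 4. How far apart could the two amounts be?** The documents state no figure, so this only shows scale.
- Session: about 4 hours (section 10.1.5), or 240 minutes.
- Collections: one minute each, every half hour. There are 8 at 0.5 to 4.0 hours into the session, or 9 if one at the start is counted. The pre- and post-dialysis samples have no stated length; one minute is assumed.
- Constant removal rate: 8/240 = 3.3% and 9/240 = 3.75% of the session amount.
- Removal rate falling with an assumed half-life of 1 hour: the session integral is (1 − 1/16)/ln 2 = 1.353, in hours times the starting rate. Nine collections sum to 3.263/60 = 0.0544, and 0.0544/1.353 = 4.0%. Eight sum to 2.263/60 = 0.0377, and 0.0377/1.353 = 2.8%.

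Summed collections thus hold about 2.8% to 4.0% of the session amount, or roughly 1/36 to 1/25.

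Section 9.4.1 fixes the dose: "Subjects will receive a single IV infusion of 200 mg MK-3866 at Hour 0 on Day 1". Suppose half of it, 100 mg, were removed (an assumption). AD,total is then 100/200 = 50% of dose. The summed collections hold 2.8 to 4.0 mg, or 1.4% to 2.0% of dose. In the same listing, CLD,dialysate × AUCD would still give 100 mg, so anyone checking the table would see the conflict.

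**The case for a change.** The strongest contrary case is that the protocol's only definition of AD is per collection, and that sections 8.1.2 and 8.2 treat AD and AD,total as different things. A programmer following the text could table the wrong one. Section 11.1.2 adds some weight: Fe in urine is defined by dividing each collection interval's amount by the dose, so a per-collection AD(%dose) has a precedent. Also, the summary statistics of a product cannot in general be rebuilt from the summaries of its factors.

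The textual mismatch stands. The rest carries less weight. AD(%dose) has no definition, so no literal reading of it exists; the summed or single-collection version is one guess among several. The one-minute length comes from the flow chart, not from the definition of AD. Section 11.1.3 does not say what dialysate volume means, and section 10.2.3 leaves the collection instructions to a separate document. The urine precedent does not carry over well, because the urine intervals adjoin and together cover 24 hours, while the dialysate collections are spot samples. That is why the plan integrates the removal rate to obtain a session amount. The point about summaries falls away because individual listings are promised, so the product can be formed per subject and then summarized. Section 11.2 also allows additional analyses, so tabulating AD,total needs no permission.

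**Conclusion.** The inconsistency is a clerical one, in a single reporting sentence. AD,total is defined, is a named endpoint, has to be computed, and can be recovered exactly from two listed quantities. No geometric mean ratio, confidence interval or dialysis clearance changes with the label. The gap of about 25 to 36 times between the summed collections and the session amount assumes a 4-hour session, 8 or 9 one-minute collections, and a removal rate that is flat or falls with a half-life no shorter than 1 hour. It also assumes a reading of AD(%dose) that the document does not state and that the rest of the list speaks against. Analysts preparing the dialysate tables would report the session amount and its percent of dose. The label could be tidied if the text is opened for another reason, but no change is needed on this account.
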